Participants will be randomized by cluster randomization (C-CBSM or CBSM) to balance treatment type across conditions. We project to retain 140 participants at our 12-months post-intervention assessment visit (T4). All participants will be asked to participate in 10-weekly 90-minute in person sessions targeting CBT based skills for managing stress and self-management in one of two experimental conditions—a linguistically translated (Spanish) and culturally adapted cognitive behavioral stress and self-management (CBSM) condition (i.e., C-CBSM) or in a standard version of CBSM that is only linguistically translated (CBSM). Following the baseline visit (T1, pre C-CBSM or CBSM), participants are randomly assigned into one of our experimental or control condition groups.

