Randomization will be group type (C-CBSM vs. CBSM) to assure balanced representation at the end of the study. The dose of both our conditions is based on our prior work documenting the efficacy of 10-week group-based programs in improving multiple psychosocial, physiological and health outcomes across multiple chronic diseases including breast cancer, HIV, CFS, CVD and localized PC (including bilingual and Spanish monolingual Hispanics) and advanced PC. Thus we feel that a 10-week involvement in our CBSM intervention balanced against the possible benefits of engaging in a supportive group environment and acquiring stress and self-management skills is reasonable for our participants. We considered a health promotion or inert usual care condition but felt that for ethical considerations, offering an inert usual care condition was not ethical. Furthermore, the conceptual approach that we are following addresses whether culturally adapted evidence-based treatments provide an added benefit with respect to improving HRQoL and reducing symptom burden, relative to standard and non-adapted programs. Therefore, because our interest is to determine whether cultural adaptation matters, we chose a comparison condition that delivers the "ingredients" of our CBT-based CBSM, but does not consider the cultural context. This approach provides a methodologically sound test of our randomized trial and the extent to which the adaptation of CBSM (C-CBSM) exerts a greater impact on our study outcomes relative to standard CBSM treatment. In our preliminary work in CBSM interventions in localized PC, our attendance at weekly sessions have been over 80%. These rates suggest that our experimental conditions delivered once a week over a 10-week period for 90 minutes per session are well accepted and tolerated in our target population.

Intervention:

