Our cultural adaptation process involved: (a) forward/back translation of CBSM; (b) review of literature on Hispanic cultural values and evidence of disparities in Hispanic PC survivors; (c) review of metaphors (e.g., concepts shared in PC), content (e.g., cultural values & traditions), illness perceptions (e.g., controllability, fatalistic themes) and context (e.g., acculturative stress, social support & ties to country of origin); (d) review of equivalence criteria of core components of the adapted EBT; (e) expert and patient review of the protocol (e.g., session by session changes); (f) focus groups; and (g) a pilot trial. 173,175,178 Based on this process and feedback from our pilot, and additional data relating sociocultural processes to symptom burden and HRQoL, we have made further modifications to our C- CBSM intervention. The full scope of adaptations to CBSM based on Hispanic cultural factors, their implications for uptake and implementation of CBSM mechanisms, and how cultural factors based on literature and expert/participant feedback are integrated in C-CBSM sessions.

Training, Intervention Fidelity & Evaluation. The MPIs and co-PIs oversee all training for recruitment and assessment staff. We have a vast pool of CBT trained facilitators, several of whom have been trained in CBSM. C-CBSM training is based on Hispanic sociocultural processes and how they interact with CBT-based programs. All group leaders will have completed a 20-hr. training seminar based on our Therapist Training Manual for C-CBSM or CBSM comprised of the following: intensive in-class training in relaxation techniques, cognitive restructuring, and assertiveness training; role-playing exercises with other staff and trained therapists with attention to adherence to protocol; and readings on group therapy/process in cancer populations. Using a standardized checklist, data is collected to document protocol adherence, identify problems at each session, and record attendance to ensure conditions are administered in the manner prescribed. ¹⁷⁹ State of the art video-conferencing platform (WebEx)¹⁸⁰

is available to the PIs and also used for clinical supervision.

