Cultural Awareness & Sensitivity Training. We will provide a 2-day training seminar on cultural sensitivity and awareness for all personnel involved in recruitment and assessment, and interventionists leading the C-CBSM condition only. To reduce contamination, interventionists in the CBSM condition do not undergo this training. To maximize participant accrual, retention and comfort with all procedures, emphasis will be on Hispanic PC survivors and involve thorough training on multicultural awareness that incorporate cultural attentiveness and sensitivity including cultural awareness (commonly held beliefs & practices by a culture), appreciation (respecting cultural differences specific to the delivery to therapeutic targets; e.g., collectivistic & familial frames of reference), and respect. 181,182,183 [name] has successfully implemented these training models in CBT-based interventions, and he is fully Spanish bilingual and has extensive experience working with Hispanics and particularly Hispanic cancer survivors.

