To Test Exploratory Hypotheses. Aim 3: For Hypotheses 3, the linear mixed model will include fixed effects for the experimental group (C-CBSM vs. CBSM) and observation time (T1-T4), and random effect for person with a compound symmetry covariance structure for the repeated residuals within person. A group by time interaction and post-hoc tests on this model effect will indicate whether and how the time course of the dependent variable differs between the groups. Hypotheses 1-3 will all be analyzed in a similar manner using the outcome measures described in sections C.6.c (Primary Outcomes), C.6.d (Intervention Targets) and C.6.e (Inflammation) respectively. These measures include markers of symptom burden, systemic inflammation, and cytokine production following cellular activation with TLR ligands. Data from gene expression profiling are analyzed using advanced bioinformatics techniques, and described in C.6.e, and as reported previously by Antoni et al.¹²⁴ As each outcome across the different study hypotheses have been carefully selected to address a priori hypotheses, no adjustment for testing of multiple outcomes will be made. However, within the analysis of a specific outcome, Tukey or Bonferroni adjustment will be made for the multiple tests across different time points. The power calculation below adjusts for this multiplicity. Aims 4a-4c: These hypotheses involve tests of proposed mediators of C-CBSM's effect on our primary outcomes. To test mediation with LGM, individual change trajectory (in each outcome of interest) is characterized by an intercept and a slope factor. The overall pattern of change (e.g., linear, quadratic, etc., as informed by analyses for Aims 1-3) for the whole group can be specified by a particular set of coefficients associated with the slope factor. First, we will specify a growth curve model for all participants with an intercept factor representing our outcome of interest at baseline, and the slope factor reflecting the change trajectory in our outcome measure from T1 to T4. For example, to test that increased stress management skills (e.g., MOCS) in the C-CBSM group accounts for reductions in symptom burden (e.g., EPIC-S), we will first test a LGM model without the stress management skills (the mediator) and then test the model with change in stress management skills from T1 to T4. In the model without the stress management skills, we expect that group assignment is not related to baseline symptom burden, but that group assignment will be related to a greater negative change (reduction) in symptom burden scores. In the next step, we will add stress management skills and expect that after adding this mediator in the model, the path between group assignment and symptom burden slope will become non-significant, while the path between the mediator and symptom burden slope is significant thus suggesting mediation. This approach will be applied to test all mediation models in hypotheses 4a-4c. 191,192 Aim 5a-5b: To evaluate moderators and mechanistic pathways of C-CBSM's effects, we will use LMM and latent variable mediation models. For Hypothesis 5a, we will test moderation by including interaction terms between group assignment (C-CBSM vs. CBSM) and each moderator of interest (e.g., SES, acculturation, Hispanic ancestry, treatment type) within the LMM framework. These models will include fixed effects for group, time (T1-T4), the moderator, and the group × moderator and group × time × moderator interactions. A significant three-way interaction (group × time × moderator) will indicate that change in the outcome (e.g., inflammation, symptom burden, HRQoL) over time differs by both treatment group and the level of the moderator. Post-hoc comparisons will clarify the nature of the moderation effects across timepoints. For Hypothesis 5b, we will test whether improvements in cardiometabolic markers (e.g., lipids, fasting glucose, blood pressure) in the C-CBSM group are mediated by reductions in inflammation using SEM. Parallel process LGMs will estimate trajectories for inflammatory markers and cardiometabolic outcomes across time. The indirect effect from group assignment to cardiometabolic outcome slope via inflammation slope will be tested. This approach allows for simultaneous modeling of changes over time, capturing both within- and between-subject effects. Model fit will be evaluated using standard criteria (CFI > .95, RMSEA ≤ .05, SRMR < .08), and significance of indirect effects will be tested using bias-corrected bootstrapped confidence intervals.

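### Group leaders appear to be nested within arm and have no term in the model, so if leaders differ the standard error of the C-CBSM versus CBSM contrast is too small; an intervention-group term fully corrects this only if each leader runs one group.

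*Combined protocol and SAP*

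**What the plan says.** **Leaders and arms.** Under Training, Intervention Fidelity & Evaluation: "All group leaders will have completed a 20-hr. training seminar based on our Therapist Training Manual for C-CBSM or CBSM". Under Cultural Awareness & Sensitivity Training, a further 2-day seminar goes to recruitment and assessment staff and, among leaders, to "interventionists leading the C-CBSM condition only". The reason follows: "To reduce contamination, interventionists in the CBSM condition do not undergo this training".

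**Where leaders come from.** "We have a vast pool of CBT trained facilitators, several of whom have been trained in CBSM". The documents give no number of leaders, no number of groups per leader and no rule for placing leaders in an arm. Random assignment is described for the men: "participants are randomly assigned into one of our experimental or control condition groups" (Randomization Protocol). That section and Experimental Design call it cluster randomization by group type and do not mention leaders.

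**Model.** Under To Test Exploratory Hypotheses, the mixed model has fixed effects for arm and time and a "random effect for person with a compound symmetry covariance structure for the repeated residuals within person". The same section extends it to Hypotheses 1-3, so it covers the primary aim. It contains no leader term and no intervention-group term.

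**Claim.** Randomization Protocol presents the comparison as a sound test of "the extent to which the adaptation of CBSM (C-CBSM) exerts a greater impact on our study outcomes relative to standard CBSM treatment".

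**The concern.** Keeping CBSM leaders out of the cultural seminar makes sense only if the two sets of leaders do not overlap. Each leader's own effect then falls wholly within one arm. Two consequences need to be kept apart.

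- **Precision.** If outcomes vary between leaders, an arm mean rests on a few leaders as well as on 100 men. A person-only model ignores this, so its standard error is too small and chance differences between leaders can pass for an effect of the adaptation. If a leader runs several groups, men in different groups share that leader, and a group random effect does not capture the link.
- **Bias.** If one arm had more skilled or more experienced leaders, the contrast would be shifted. Randomising men does not prevent this, and no variance term removes it.

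The influence need not end with the sessions. Under Preventing Attrition and Reducing Burden, group facilitators also make booster calls between T2 and T4. The stake is the trial's central claim, the added value of cultural adaptation over translation alone.

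**Working it through.** **Plan's own figures.** Power Analyses gives 80% power at 0.40 SD with 100 per arm (two-sided 5%), and a detectable 0.49 SD at 1%. For independent men the standard error is √(2/100) = 0.1414.

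- At 5%: 0.40/0.1414 − 1.96 = 0.87, power 80.7%.
- At 1%: 0.49/0.1414 − 2.576 = 0.89, power 81.3%.

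Both figures reproduce, with no variance allowed for leaders or groups.

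**Inputs.**

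- From the documents: 100 men per arm; 140 men projected at T4, so 70 per arm; groups of 4-8 men, so 100/8 to 100/4, or about 13-25 groups per arm.
- Assumed: 17 groups per arm (about 100/6); J = 4 or 8 leaders per arm; leader share of variance ρ = 2%-5%; no separate group variance.

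**Formulas**, in units of total variance, for one arm mean:

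- true variance: ρ/J + (1−ρ)/n
- person-only model: 1/n
- model with a group term: ρ/17 + (1−ρ)/n
- true error of a nominal 5% test: 2[1 − Φ(1.96 √(model variance / true variance))]

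Example with J = 4, ρ = 0.05, n = 100: true variance = 0.0125 + 0.0095 = 0.0220. Person-only: √(0.0100/0.0220) = 0.674, so 1.96 × 0.674 = 1.32 and the error is 18.6%.

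| Leaders per arm | ρ | Person-only, n = 100 | With group term, n = 100 | Person-only, n = 70 |
|---|---|---|---|---|
| 4 | 2% | 10.7% | 9.1% | 8.9% |
| 4 | 5% | 18.6% | 14.1% | 14.7% |
| 8 | 2% | 7.7% | 6.4% | 6.8% |
| 8 | 5% | 11.8% | 8.2% | 9.6% |
| 17 (one group each) | 2%-5% | 6.1%-7.9% | 5.0% | 5.7%-6.8% |

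At a 1% share with 8 leaders, the person-only error at 100 per arm is 6.3%.

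**Simulation check** (20,000 runs, 16 groups of 6 per arm, no true effect, one change score). With 4 leaders the person-only and group-term errors were 10.5% and 9.0% at ρ = 2%, and 18.3% and 14.1% at ρ = 5%. A leader-level test held about 5% throughout. With one leader per group, the group term alone also held about 5%.

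**Hypothetical bias.** If C-CBSM leaders were better by b SD and the adaptation did nothing, the chance of a false C-CBSM win is 1 − Φ(1.96 − b√(n/2)). At 100 per arm this is 10.5% for b = 0.1 and 29.3% for b = 0.2. At 70 per arm it is 8.6% and 21.9%. No source in the documents supports any value of b.

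**Cost in power.** Take a t-test with leader as the unit, 2J − 2 degrees of freedom, and noncentrality 0.40/√(2[ρ/J + (1−ρ)/100]). With 4 leaders (6 df) power is about 66% at ρ = 0, 50% at 2% and 36% at 5%. With 8 leaders (14 df) it is about 66% at 2% and 55% at 5%.

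**The case against.** **Silence is not evidence.** A reader might infer that leaders are placed by choice, that each runs many groups, or that the C-CBSM leaders are the stronger set. The documents support none of these; they are silent. The remark about prior CBSM training shows an uneven pool, not uneven arms. A large pool also leaves room for one leader per group, and then an intervention-group term is enough. This stands, so the point has to be conditional.

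**Quality control exists.** All leaders take a 20-hour training with role-play and attention to protocol adherence. A checklist is completed at each session, there is clinical supervision, and sessions may be recorded with consent. These measures may reduce leader differences, but they put nothing into the standard error. The cohort ANOVA planned under Covariates, Cohort Effects, Intent to Treat & Missing Data compares cohorts, does not name leaders, and does not correct the standard error either.

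**Cultural training is part of the intervention.** True: its effect is intended and is not a confounder. Leaders' general skill and earlier CBSM experience are not part of the adaptation, however, and the claim in Randomization Protocol does not separate them.

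**The remedy has limits.** Random allotment may come too late. The protocol's effective date is 8/14/2025, and Data and if applicable, Specimen Banking refers to data already collected and transferred. Risks mentions one of the interventionists contacting a distressed participant after a session, so co-led groups are possible, and simple nesting of groups under one leader would not fit them.

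**Conclusion.** The concern holds in conditional form. Leaders appear to be nested within arm, and the model for Hypotheses 1-3 has neither a leader nor a group term. If leaders differ, the standard error of the arm contrast is too small. This does not depend on how leaders were allotted: a small number of randomly placed leaders would have the same effect on precision.

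Under a 2%-5% leader share, the true error of a nominal 5% test is about 11%-19% with 4 leaders per arm and 8%-12% with 8, at 100 men per arm. At 70 per arm it is about 9%-15% and 7%-10%. A group term alone leaves part of the excess if leaders run several groups, and none if each runs one. The leader share and the number of leaders are assumptions; the documents supply neither.

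The tempting stronger conclusion, that the contrast is biased by better leaders in one arm, is not supported. Such a bias is possible and the design as described does not rule it out, but the documents do not show that one exists.

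**What to change.** 1. **Record** leader identity (both leaders if co-led) and prior CBSM experience for every group.
2. **Pre-specify**, alongside an intervention-group term, an analysis of Hypotheses 1-3 with a random leader effect on the post-baseline visits and small-sample degrees of freedom. Use a multiple-membership form if groups are co-led. Report the number of leaders per arm and results by leader.
3. **Limit the claim** in Randomization Protocol: the contrast tests the adapted manual as delivered by its own culturally trained leaders. Do not attribute a difference to the adaptation alone if it does not survive the leader-level analysis.
4. **For leaders not yet trained**, allot them to arms at random, stratified by prior CBSM experience.

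Recording and rewording cost little. The leader-level analysis widens the intervals and, if leaders are few, lowers power materially, as the power figures above show. It corrects precision only. A systematic difference between the two sets of leaders can be guarded against only by random allotment; where leaders are already in place, it has to be reported as a limitation.
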